# **6. ASSESSMENT VARIABLES**

## **6.1. Demographics**

Demographics, including presenting symptoms, primary diagnosis, concomitant medical problems, and treatment history, will be collected from the information recorded at the Pre-Application interval.

## **6.2. Wound Assessment**

Wounds will be assessed through gross observation and analysis for signs of infection, wound progression, and tissue healing. Gross observation will be utilized

to determine the necessity of graft reapplication or standard dressing change. Wound area measurements will be conducted via acetate tracings.

### **6.3. Safety**

See section 8 for safety assessment information.

## **7. ADVERSE EVENT (AE)**

### **7.1. Principal Investigator Responsibilities**

The Principal Investigator (PI) and/or staff participating in the study shall document all adverse events as defined in section 7.3 of this protocol. The severity of the AE and its relationship to the procedure / device will also be assessed by the PI. The PI will document on the CRF any relatedness descriptions that might apply to the AE (e.g. none, possible, probable, and definite). The sponsor will designate a monitor to review patient medical records at the study locations for indications of adverse events throughout the study to ensure appropriate documentation and reporting.

Reimbursement data collected in the study requires purchase of the Restrata™ material so that the investigator is able to submit for reimbursement from payers. The purchase price will be agreed upon within the Clinical Trial Agreement.

### **7.2. Preexisting Conditions**

In this study, a preexisting condition (i.e., present before the adverse event reporting period started that are noted on the preop medical history form) should not be reported as an adverse event.

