## 2. INTRODUCTION & PURPOSE

### 2.1. Background and Purpose

The process of wound healing requires a coordinated effort of cellular recruitment and tissue growth. Regenerative matrix materials have been used to promote this coordination and provide immediate wound coverage to minimize the risks associated with infection and fluid loss. An ideal material for these purposes would serve as a healing scaffold, limit infection risk, minimize inflammation, be readily available for use, and be conformable to diverse wound surfaces. [1,2]

Human autografts and allografts, animal-based xenografts, and fully synthetic materials have been used clinically with varying degrees of success. Autograft availability is limited by definition, and creates iatrogenic morbidity at donor sites. Allografts and xenografts eliminate the morbidity associated with autografts, but introduce additional risks of inflammatory response and disease transmission. Furthermore, host rejection of allografts and xenografts remains a concern in wound populations where the rate of immune disease has been reported as high as 23%. [3]

To support the infiltration of fibroblasts, the deposition of new collagen, and re-epithelialization of the wound surface, the wound matrix material should persist in the wound for at least three weeks. [4] The timing of wound matrix degradation is therefore critical, as the wound matrix should resist degradation until sufficient new tissue growth has occurred. The susceptibility of biologic wound matrix materials to enzymatic degradation leads to a resorption rate that is poorly controlled, risking the premature degradation of the wound matrix prior to sufficient wound healing. [5]

There remains a need for materials that minimize inflammation and promote complete wound healing. [6,7,8] Electrospun fibrous scaffolds may meet this need by mimicking the structure of native extracellular environment while enabling resident cells to perform their roles in the healing cascade. [9,10] The purpose of the following study is evaluate the initial safety and effectiveness of Restrata™ Wound Matrix in treating diabetic foot ulcers in human subjects, and to inform the design of a randomized controlled trial of Restrata™ Wound Matrix

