## 4. PATIENT SELECTION

### 4.1. Inclusion Criteria

- Male or female age 18 or older
- Patient's ulcer must be diabetic in origin, located at least in part on the plantar surface and larger than 1cm^2 after the run-in period. Debridement will be done prior to randomization. Subject's informed consent for participating in this study, must be obtained prior to proceeding with sharp debridement
- Patients with Type 1 or Type 2 diabetes (criteria for the diagnosis of diabetes mellitus per ADA).
- Ulcer must be present for a minimum of four weeks before enrollment/randomization, with documented failure of prior treatment to heal the wound. A two-week run in period will precede enrollment/randomization in the trial to document the indolent nature of the patients selected
- Patient does not exhibit clinical signs / symptoms of infection upon gross observation (at least 3 of the following: pain, redness, purulence, exudate, temperature) or have been diagnosed with an active infection at time of screening
- Patient is willing to provide informed consent and is willing to participate in all procedures and follow up evaluations necessary to complete the study
- Patient has adequate control of diabetes, as demonstrated by one of the following within 30 days of screening:
  - HbA1c < 12%

- Serum Creatinine < 3.0mg/dl
- Patient has adequate circulation to the affected extremity, as demonstrated by one of the following within the past 60 days of the first screening visit:
  - Dorsum transcutaneous oxygen test (TcPO2) with results  $\geq 30$ mmHg, OR
  - ABIs with results of  $\geq 0.7$  and  $\leq 1.5$ , OR
  - Doppler arterial waveforms, which are triphasic or biphasic at the ankle of affected leg

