### **7.3. Adverse Event Definitions**

#### **7.3.1. Device Related Adverse Event (AE)**

A device related adverse event is any undesirable untoward response to the medical device experienced by a patient during the course of the study.

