### 7.3.2. Serious Adverse Event (SAE)

A serious adverse event is any undesirable adverse event or untoward medical occurrence (sign, symptom, illness, abnormal laboratory value, or other medical event) experienced by a patient during the course of the study that:

- Results in death;
- Is life-threatening;
- Requires inpatient hospitalization or prolongation of an existing hospitalization;
- Results in persistent or significant disability/incapacity;
- Requires intervention to prevent a permanent impairment of a bodily function or damage to a body structure.

Medical and scientific judgment should be exercised in determining whether an event is an important medical event. An important medical event may not be immediately life-threatening and/or result in death or hospitalization. However, if it is determined that the event may jeopardize the patient and may require intervention to prevent one of the other outcomes listed in the definition above, the important medical event should be reported as serious.

Examples of such events are intensive treatment in an emergency room for a bronchospasm or convulsions that do not result in hospitalization.

This definition of an SAE is not intended to include hospitalization specifically to treat a condition that existed prior to the patient's enrollment in the study (e.g., pre-existing cardiovascular disease that is treated during the study) or prearranged elective surgery performed during this study period.

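### Sections 7.2 and 7.3.2 make no exception for worsening, so deterioration of the index ulcer, or an unplanned admission to treat it, can be left out of the safety tables

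*Combined protocol and SAP*

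**What the plan says.** Section 7.2 defines a pre-existing condition as one "present before the adverse event reporting period started that are noted on the preop medical history form", and says that it "should not be reported as an adverse event". Section 7.3.2 lists the seriousness criteria and then states that the SAE definition is "not intended to include hospitalization specifically to treat a condition that existed prior" to enrollment. Its example is cardiovascular disease treated during the study. Prearranged elective surgery follows as a separate item.

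The only other AE definition is in section 7.3.1, which is limited to device-related events: "any undesirable untoward response to the medical device experienced by a patient during the course of the study". Section 7.1 tells the investigator to document AEs as section 7.3 defines them.

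The index ulcer falls within these rules through the inclusion criteria in section 4.1: "Ulcer must be present for a minimum of four weeks before enrollment/randomization". Section 2.1 says the study is to "evaluate the initial safety and effectiveness" of the device. For safety, section 8.1 plans only a tabulation of AE rates by type, severity and relatedness.

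**The concern.** In a study of a wound device, deterioration of the treated wound is one of the first things a safety reader looks for. Here that wound is itself a pre-existing condition in every patient. A rule that keeps pre-existing conditions out of AE reporting, without adding the exception for worsening, can remove those events from the tables. The loss runs in one direction, because omission can only lower the reported rate.

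Initial safety is a stated purpose, the results are meant to inform a randomized trial, and device safety concerns are a ground for termination in section 12. There is no control arm against which a shortfall in reporting might be noticed. An event that was never entered as an AE is also hard to recover reliably once data collection is over.

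**Working it through.** The documents attach no figure to this point, so the main check is to set the rules side by side.

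1. **Is the index ulcer pre-existing under section 7.2?** It must have been present for at least four weeks before enrollment (section 4.1). Appendix A starts the AE form at Week 0, after the run-in. Section 6.1 records primary diagnosis and concomitant problems before application, and Appendix A places the medical history form at the first visit. The form itself is not in the documents. Assuming that it notes the ulcer, the ulcer meets the definition in every patient.

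2. **Is there an exception for worsening?** There is none in section 7.2 or 7.3.2, or elsewhere in the protocol.

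3. **Is the exclusion in section 7.3.2 limited to planned admissions?** No. Prearranged elective surgery is a separate alternative, and the cardiovascular example concerns treatment during the study. An unplanned admission specifically to treat a worsening study ulcer is therefore outside the hospitalization criterion as written.

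4. **What stays reportable as serious?** The exclusion concerns hospitalization only, apart from prearranged surgery. Death, life-threatening events, disability, important medical events and the criterion "Requires intervention to prevent a permanent impairment of a bodily function or damage to a body structure" remain. The exposed case is an admission that meets no criterion except hospitalization.

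5. **Does section 7.3.1 bring non-serious worsening back?** Only if the site judges it a response to the device, and section 7.2 would still tell the site not to report it. The two sections conflict, and relatedness then decides whether an event is counted at all, although section 8.1 intends relatedness as a column of the table.

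6. **Are complications new events?** Section 4.1 bars clinically infected ulcers at entry, section 4.2 bars ulcers probing to bone, and section 3 names infection as an example of an AE. Later infection or bone involvement is arguably new and reportable. A site could still record the admission as treatment of the pre-existing ulcer, and the text does not settle which is right.

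**Illustration of scale.** The documents give no rate of ulcer worsening or related admission. The counts below are assumptions, with n = 30 from section 3. For x events in n patients, the exact (Clopper-Pearson) 95% limits are the 0.025 quantile of Beta(x, n − x + 1) and the 0.975 quantile of Beta(x + 1, n − x). For x = 0 the lower limit is 0 and the upper limit is 1 − 0.025^(1/30) = 0.116.

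| Patients with such an admission | Rate | Exact 95% CI |
|---|---|---|
| 0 | 0/30 = 0% | 0 to 11.6% |
| 1 | 1/30 = 3.3% | 0.1 to 17.2% |
| 2 | 2/30 = 6.7% | 0.8 to 22.1% |
| 3 | 3/30 = 10.0% | 2.1 to 26.5% |

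If all such admissions were omitted, the first row would be reported whichever of the other rows was true. That is the worst case: it needs every site to read both rules literally, and every admission to meet no other criterion.

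**The case against.** The strongest reply is that section 7.2 describes the condition as it stood at baseline and is merely silent about later change. On that view this is an ambiguity, not a rule that drops events. Major complications would mostly be new events, since infected and bone-probing ulcers are barred at entry. Section 7.4 grades loss of limb as severe, so limb loss is evidently expected to be reported. Wound area is traced weekly, photographs and infection checks are made at follow-up visits, and a monitor reviews medical records for AEs. The study is a small descriptive series whose primary outcome, wound closure, is unaffected.

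Much of this stands. A reader might infer that worsening of the index ulcer is excluded outright and can never be an AE or SAE. The documents do not support that: section 7.2 omits worsening without naming it, and section 7.3.2 leaves every other route to seriousness open. A reader might also take three lost events in 30 as an estimate, and it is not one.

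Two things do not fall to the reply. The hospitalization exclusion in section 7.3.2 is a stated rule, not silence, and it reaches unplanned admissions for the ulcer. The other data collection does not replace AE reporting either. Wound tracings give size as an effectiveness outcome, without admission, severity or relatedness, and the monitor would be checking records against the same definitions.

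**Conclusion.** The point holds in this limited form. As written, sections 7.2 and 7.3.2 allow deterioration of the index ulcer, and unplanned admissions to treat it that meet only the hospitalization criterion, to be left out of the AE and SAE tables or handled differently from site to site. The bias in the reported rates is downward, and those rates are the only safety output planned. Its size cannot be estimated from the documents; with 30 patients, even one to three omitted events would visibly change the reported rate.

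The conclusion assumes that the history form notes the index ulcer and that at least some sites apply the rules literally. It does not extend to deaths, life-threatening events, disability, intervention to prevent permanent impairment, important medical events, or new infection or bone involvement, all of which can still be reported. The closure endpoint is not affected.

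**What to change.** - **Section 7.2:** state that a pre-existing condition, including the study ulcer, is reported as an AE if the investigator judges that it has worsened from baseline after the first device application. Resting this on the investigator's judgement avoids turning every small rise in traced area into an AE.
- **Section 7.3.2:** limit the hospitalization exclusion to admissions planned before enrollment, or for a pre-existing condition that has not worsened. State that unplanned hospitalization for the study ulcer or its complications is reported.
- **Sections 7.1 and 7.3.1:** reconcile these with the above. At present non-serious events are defined only as device-related, so changing section 7.2 alone would leave worsening judged unrelated outside the definition. Such worsening should be recorded whatever its judged relatedness, with relatedness kept as a tabulated attribute.

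The cost is a few sentences in the protocol and the matching form instructions, slightly more reporting work at sites, and a somewhat higher reported AE and SAE rate. Treatment and the effectiveness analysis do not change.

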### **7.3. Adverse Event Definitions**

#### **7.3.1. Device Related Adverse Event (AE)**

A device related adverse event is any undesirable untoward response to the medical device experienced by a patient during the course of the study.

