### **Tertiary Outcome Measures:**

- Quality of Life- Odor reduction [ Time Frame: Baseline (0 weeks), 4 weeks, 8 weeks, 12 weeks ]

- Quality of Life- Itch reduction [ Time Frame: Baseline (0 weeks), 4 weeks, 8 weeks, 12 weeks ]
- Quality of Life- Visual appearance
- Number of reapplications / Size of units applied
- Incidence of adverse events (e.g. infection, etc.)
- Cost effectiveness / Economic model (Amount of product usage, length of treatment)
- Intraoperative notes / Ease of Use, Handling (Feedback on handling / ease of use and placement)
- Billing / Coding / Reimbursement information

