## **5.5. Adverse Event Assessments**

Assessment of safety is documented on the Adverse Events forms. The investigator should document any reported adverse events that occur outside of interval visits. Documentation of Adverse Events should include type, severity and relatedness to the device.

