# 8. DATA ANALYSIS

## 8.1. Demographics and Outcomes

Descriptive statistics will be used to compare amongst experimental groups, along with confidence intervals where appropriate to measure effect size. Rates of adverse events will be tabulated by type, severity and device / procedure relatedness. Furthermore, statistics on the wound measurements over time and at the 12 week endpoint will be used to inform future study hypotheses.

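### Section 7.3 defines no non-serious adverse event except a response to the device, which conflicts with sections 5.5, 7.1 and 8.1 and leaves it unclear whether unrelated non-serious events, including infections, are counted

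*Combined protocol and SAP*

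**What the plan says.** Section 7.1 sets the capture rule: the investigator and staff "shall document all adverse events as defined in section 7.3 of this protocol". Section 7.3 then holds two definitions.

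- **Events linked to the device (7.3.1):** "A device related adverse event is any undesirable untoward response to the medical device experienced by a patient during the course of the study".
- **Events that are serious (7.3.2):** "A serious adverse event is any undesirable adverse event or untoward medical occurrence" that meets one of the listed seriousness criteria. No link to the device is needed.

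Other parts of the protocol describe a wider set of events.

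- **7.1** has the investigator judge the relationship to the procedure as well as the device, and enter on the case report form (CRF) "any relatedness descriptions that might apply to the AE (e.g. none, possible, probable, and definite".
- **5.5** says: "The investigator should document any reported adverse events that occur outside of interval visits". It also lists relatedness among the details to be recorded for each AE.
- **8.1** says: "Rates of adverse events will be tabulated by type, severity and device / procedure relatedness".
- **Section 3** lists as a tertiary outcome "Incidence of adverse events (e.g. infection, etc".

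Separately, section 5.2 (wound assessment) and section 5.4 have sites record signs of infection and inspect the wound for infection at follow-up visits. Appendix A schedules the wound assessment CRF and photograph from Week 0 onward.

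**The concern.** Relatedness should be judged after an event has been captured. Under 7.1 read with 7.3.1, it becomes the condition for capturing a non-serious event. An outpatient wound infection put down to poor off-loading, or a blister put down to the boot, meets neither definition in 7.3.

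Initial safety is a stated purpose in section 2.1, and AE incidence is a listed outcome. There is no control group and only the subject is masked (section 3), so every investigator knows that every patient has the device. If the definition is taken at its word, the non-serious rate reflects each investigator's causal opinion. If some of the up to 8 sites follow 7.3 and others follow the relatedness scale, the pooled rate mixes two definitions. An event that was never entered on the AE form cannot be recovered by tabulating differently later.

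**Working it through.** The plan states no AE rate, so there is no figure to reproduce. The check sets the definitions against the rules that use them.

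**Step 1: which events 7.3 admits.** Classify events by seriousness and by the investigator's view of cause.

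| Event | Meets 7.3.1? | Meets 7.3.2? | Must be documented under 7.1, read literally? |
|---|---|---|---|
| Serious, judged related to the device | Yes | Yes | Yes |
| Serious, judged unrelated or procedure-only | No | Yes | Yes |
| Non-serious, judged a response to the device | Yes | No | Yes |
| Non-serious, judged unrelated or procedure-only | No | No | No |

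Only the last row falls outside. The all-cause wording used for serious events has no counterpart for non-serious ones.

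**Step 2: what the other sections assume about that row.** A grade of none (7.1) has no use for a non-serious event if 7.3.1 decides what is entered. Neither does a judgement of procedure-only relationship (7.1, 8.1). Section 5.5 treats relatedness as something recorded about an AE, not as a test for being one. All three presuppose that events in the last row are on file. The two sets of instructions cannot both be followed.

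**Step 3: whether any text settles it.**

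- The sentence in 5.5 on reported events concerns those arising outside interval visits, and gives no definition.
- The monitor described in 7.1 reviews records for AEs, again with only 7.3 to say what an AE is.
- Section 6.3 sends the reader to section 8 for safety, and section 8 defines no event.
- Section 7.5 leaves reporting to each review board's procedures, which may differ between sites.

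**Step 4: infection.** Its signs are recorded at wound assessment whatever the presumed cause. But 5.5 places the safety assessment on the AE forms, and 8.1 tabulates AEs. No rule turns recorded signs into an infection event, and no infection criterion is given for follow-up. Section 4.1 has one for entry: at least 3 of 5 listed signs, or a diagnosed active infection.

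**Step 5: size.** Let S be the number of patients with any serious event. Let R be the number with no serious event but at least one non-serious event judged a response to the device. Let U be the number whose only events are non-serious and not so judged.

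- All-cause count = S + R + U.
- Count under the literal rule = S + R.
- Shortfall = U.

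With 30 patients, each patient in U lowers the reported incidence by 1/30 = 3.3 percentage points. The documents give nothing from which U can be estimated. It could be zero if every site records all-cause events.

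**The case against.** The strongest reply is that the protocol as a whole points to all-cause capture. It has a grade of none, a procedure relationship, a request for any reported event, a monitor reviewing records with no stated relatedness filter, and a table by relatedness. On this view 7.3.1 is a loosely drafted subset definition, and sensible sites will record everything.

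Much of this stands, and it rules out three stronger readings that a reader might infer.

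- **That AE incidence covers only events attributed to the device.** It does not: serious events enter whatever their cause, and several sections expect unrelated events.
- **That infections judged unrelated are missing from the data.** Their signs should be in the wound assessment record even if the AE table omits them.
- **That the reported rate is certainly too low and will mislead the planned randomized trial.** A low rate depends on sites following the narrow rule. What 8.1 says will inform future hypotheses is the wound measurements, and the plan specifies no comparison of AE rates with published rates.

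It is also fair that AE incidence is a tertiary outcome in a small descriptive series.

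The reply does not remove the conflict. The one sentence that says which events must be documented points to 7.3, and 7.3 omits the category that the other sections assume.

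**Conclusion.** The point holds for non-serious events. Section 7.3 has no general definition of them. Its only non-serious definition, applied literally through 7.1, leaves out those judged unrelated or procedure-only, contrary to the relatedness grading in 7.1, to 5.5 and to 8.1. Non-serious AE incidence could therefore vary with investigator attribution and between sites, and any resulting error relative to an all-cause count is downward. For infection, the remaining gap is that neither the source nor the criterion for the incidence is stated.

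The size cannot be estimated from the documents. The conclusion rests on the text alone, plus the assumption that at least some sites would apply 7.3 as written. It merits correction before data collection, because events left off the AE form cannot be restored at analysis.

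**What to change.** 1. **Section 7.3:** open with a general definition. An AE is any untoward medical occurrence in an enrolled patient, whether or not it is considered related to the device or the procedure. Keep 7.3.1 as the related subset. Section 7.2 on preexisting conditions can stay as it is.
2. **Section 8.1:** tabulate all AEs first, then the subset related to the device or procedure.
3. **Infection:** state that the incidence is counted from the wound assessment and AE records together, independently of attribution. Use the full entry criterion in 4.1, meaning at least 3 of the 5 listed signs (pain, redness, purulence, exudate, temperature) or a diagnosed active infection. The wound assessment form should show each sign separately so that the threshold can be applied.

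The cost is one definition in an amendment, a few form fields and somewhat more AE entries. The reported rate may look less favourable. In return, 5.5, 7.1, 7.3 and 8.1 would describe the same set of events.
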